The mechanism of oncogenesis from high-risk HPV infection in squamous mucosal epithelium is consistent, whether the site of infection is the cervix or the oral or anal mucosa. Persistence of the virus and its inhibition of tumor suppressor functions can lead to the development of dysplasia or malignant carcinoma. Anorectal cancer, although relative rare has been steadily increasing over the last 50 years. And while both survival and locoregional control is good for patients with early stage anorectal cancer, for those patients with high risk and/or recurrent metastatic disease the unmet medical need remains high.[8, 9] The epidemiology of anorectal cancer demonstrates that high-risk HPV has been reported in approximately 90% in patients with squamous cell cancer of the anorectal canal, with serotypes HPV 16 and 18 being the most common.[10] Given the activity that ADXS11-001 has demonstrated in metastatic squamous cell cancer of the cervix,[3] which are histologically and epidemiologically similar to anorectal cancer, evaluation of ADXS11-001 in patients with anorectal cancer seem logical.

[figure not shown]
Currently there is an ongoing clinical study in subjects with high-risk locally advanced squamous anal cancer which evaluates ADXS11-001 therapy prior to, and following standard of care radiotherapy and concurrent 5FU/mitomycin C (MMC) (NCT #01671488). To date 10 subjects have been enrolled. Preliminary safety data from this ongoing study are consistent with those observed with ADXS11-001 treatment to date. The current study seeks to evaluate ADXS11-001 in the metastatic population. The standard of care for patients with metastatic disease was established several years ago with a combination regimen of 5FU and cisplatin. Response rates with this combination range between 40-50% with median overall survival of 34.5 months.[11, 12] While efficacious, patients will recur and eventually succumb to their disease. The need to evaluate new therapies, particularly those targeted at HPV, such as ADXS11-001 is warranted.

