5 METHODOLOGY

5.1 Entry Criteria

5.1.1 Inclusion Criteria

This study will include subjects with persistent/recurrent, loco-regional or metastatic SCCA of the anorectal canal.

For subjects to be eligible they:

1. Must have histopathologic diagnosis of squamous cell cancer of the anorectal canal.
 2. Must have received at least one line of therapy for their metastatic disease. However patients deemed by their investigator as not optimal candidates for chemotherapy (e.g., drug allergy, ototoxicity, renal insufficiency) would be considered eligible.
 3. Be willing and able to provide written informed consent for the trial.
 4. Be ≥ 18 years of age on day of signing informed consent.
 5. Have measurable disease based on RECIST 1.1
 6. Have Eastern Cooperative Oncology Group (ECOG) performance status of 0 or 1.
 7. Demonstrate adequate organ function as defined in [Table 3](#).
-

Table 3 Adequate Organ Function Laboratory Values

System	Laboratory Value
Hematological	
Absolute neutrophil count (ANC) ^a	≥1,000 /mcL
Platelets	≥75,000 / mcL
Hemoglobin	≥9 g/dL or ≥5.6 mmol/L
Renal	
Serum creatinine OR Measured or calculated ^b creatinine clearance (GFR can also be used in place of creatinine or CrCl)	≤1.5 X upper limit of normal (ULN) OR ≥50 mL/min for subject with creatinine levels >1.5 X institutional ULN
Hepatic	
Serum total bilirubin	≤1.5 X ULN OR Direct bilirubin ≤ULN for subjects with total bilirubin levels >1.5 ULN
AST (SGOT) and ALT (SGPT)	≤2.5 X ULN OR ≤5.0 X ULN for subjects with liver metastases
Coagulation	
International Normalized Ratio (INR) or Prothrombin Time (PT)	≤1.5 X ULN unless subject is receiving anticoagulant therapy as long as PT or INR is within therapeutic range of intended use of anticoagulants
Activated Partial Thromboplastin Time (aPTT)	≤1.5 X ULN unless subject is receiving anticoagulant therapy as long as aPTT is within therapeutic range of intended use of anticoagulants
^a ANC, Platelets, Hemoglobin requirement cannot be met by the use of recent transfusions, or growth factor support (G-CSF, erythropoietin, etc) within 2 weeks prior to treatment initiation.	
^b Creatinine clearance should be calculated per institutional standard.	

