8. Female subjects of childbearing potential must not be breastfeeding and have a negative urine or serum pregnancy test within 72 hours prior to receiving the first dose of study medication. If the urine test is positive or cannot be confirmed as negative, a serum pregnancy test will be required.
9. Female subjects of childbearing potential should be willing to use 2 methods of birth control for the course of the study through 120 days after the last dose of study medication (see [Section 5.7.2](#)).
10. Male subjects should agree to use an adequate method of contraception starting with the first dose of study therapy through 120 days after the last dose of study therapy.
11. Must have a washout period of the following prior to first dose of study treatment:

- a. **14 days** from completing prior standard of care therapy, with the exception of MMC and palliative radiation therapy for disease-related pain.
- b. **6 weeks** from the last dose of MMC, given the delayed bone marrow suppression that can be experienced with MMC.
- c. **28 days** from treatment with investigational device/therapy or 3 times the half-life in the case of monoclonal antibodies, whichever is longer
- d. **7 days** from treatment with systemic steroid therapy or any other form of immunosuppressive therapy
- e. **30 days** from treatment with live vaccine

Note: Examples of live vaccines include, but are not limited to, the following: measles, mumps, rubella, chicken pox, yellow fever, rabies, BCG, typhoid, and intranasal influenza vaccines (e.g., Flu Mist®). Seasonal influenza vaccines for injection are generally killed virus vaccines and are allowed.

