5.5.2 Prohibited Concomitant Therapies

Subjects are prohibited from receiving the following therapies during the Screening and Treatment Phase of this trial:

- Anti-cancer therapy including but not limited to, hormonal, chemotherapy, radiation therapy, treatment with targeting agents (eg, Tyrosine kinase inhibitors). However occasional radiation therapy for palliation of pain is allowed
 - Note: Radiation therapy to a symptomatic solitary lesion or to the brain may be allowed after consultation with Sponsor. Radio-pharmaceuticals (e.g., radium, strontium, etc.) are not acceptable.
 - Immunotherapy not specified in this protocol
 - Investigational agents other than ADXS11-001
-

- PI3K inhibitors and TNF α blocking agents
- Live vaccines (eg, measles, mumps, rubella, chicken pox, yellow fever, rabies, BCG, and typhoid) and intranasal influenza vaccines (eg, Flu-Mist®). Seasonal influenza vaccines for injection are generally killed virus vaccines and are allowed.
- Chronic use of systemic glucocorticoids has the potential to reduce the immune response therefore should not be used. However, glucocorticoids should be considered to manage symptoms related to cytokine release. Topical use of steroids is allowed. The intermittent use of steroids for the treatment of COPD and or asthma is allowed.
- Anti-infectives should be avoided. However, subjects with a documented infectious complication should receive oral or IV antibiotics or other anti-infective agents as considered appropriate by the treating investigator for a given infectious condition, according to standard institutional practice.
- Acetaminophen is not to be used for premedication because it does not have anti-inflammatory properties required for AE amelioration but may be used for supportive care measures.

Subjects who, in the assessment by the investigator, require the use of any of the aforementioned treatments for clinical management may be removed from the trial after discussion with the sponsor. Subjects may receive other medications that the investigator deems to be medically necessary.

The Exclusion Criteria ([Section 5.1.2](#)) describe other medications that are prohibited in this trial. There are no prohibited therapies during post-treatment follow-up.

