⁸ All Subjects will receive a 7-day course of oral antibiotic therapy starting approximately 72 hours after administration of ADXS11-001. All subjects will also receive an additional 6 month oral antibiotic course to be initiated approximately 72 hours following the last dose of study treatment or anytime upon discontinuation of study treatment.

⁹ Adverse events and serious adverse events will be assessed from the time Informed Consent is obtained through 30 days after the last ADXS11-001 infusion is administered.

¹⁰ Height will be measured at screening only. Monitor vital signs immediately [REDACTED] for the first 4 hours following the completion of every ADXS11-001 infusion.

¹¹ CID1 Safety labs do not need to be repeated if screening labs are collected within 3 days of dosing. All laboratory procedures are to be completed and assessed by the investigator within 3 days prior to the administration of ADXS11-001 to confirm lab criteria for study treatment are met.

¹² Urine pregnancy tests must be performed within 72 hours prior to each ADXS11-001 infusion for female subjects of childbearing potential. If the urine test is positive or cannot be confirmed as negative, a serum pregnancy test will be required.

¹³ *Lm* Surveillance Monitoring will include a 6-month course of oral antibiotics and routine monitoring of CBC, CMP (including CRP, ESR) and blood cultures. Following completion of the last dose of study treatment or following study discontinuation, all assessments will be performed every 4 months (±2 weeks) for 3 years.

¹⁴ Baseline tumor imaging and assessments must be performed within 28 days prior to the first ADXS11-001 infusion in the first study cycle. Subsequent tumor imaging and assessments will be conducted at Week 8 (±1 week) for the duration of study participation. Radiologic progression, not accompanied by clinical deterioration, should be confirmed ≥4 weeks later.

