7.1.6.1 Screening

Screening period – will start when the first screening evaluation is performed. This does not include signing of informed consent or wash out periods. Screening evaluations will be performed within 28 days prior to the first treatment administration, unless otherwise specified.

Informed Consent - each subject must sign a copy of the most current IRB/IEC approved informed consent document. A copy of the signed document will be maintained with the subject's records.

Inclusion/Exclusion Criteria - all inclusion and exclusion criteria will be reviewed by the Investigator or qualified designee to ensure that the subject qualifies for the trial.

Prior/Concomitant Therapies and Procedures - past or current medical conditions, current medications, medications taken within 28 days of study entry, histological confirmation of cancer, tumor staging (refer to the most current American Joint Committee on Cancer Staging Manual, the 5th edition or higher), and prior cancer therapies and best response(s), if applicable.

Pregnancy test - A rapid pregnancy test will be performed for all women of child bearing potential. A positive rapid pregnancy test must be confirmed by serum pregnancy test (minimum sensitivity 25 IU/L or equivalent units of β HCG).

Laboratory Procedures (hematology, chemistry, urinalysis, other) – see [Section 7.1.3](#).

Tumor Imaging/Disease Assessment - CT scan or MRI for determination of unidimensional measurements and disease response. Baseline tumor imaging/disease assessment must be performed within 28 days prior to the first dose of ADXS11-001. Then imaging studies and tumor assessments will be performed every 9 weeks starting on Week 8 of every Cycle.

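### A target lesion irradiated for pain after the baseline scan can still produce a counted partial response, because palliative radiation has no stated washout and no response rule covers it

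*Combined protocol and SAP*

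**What the plan says.** **Washout (5.1.1 #11).** Fourteen days are required "from completing prior standard of care therapy, with the exception of MMC and palliative radiation therapy for disease-related pain". MMC has its own six-week interval, counted "from the last dose of MMC, given the delayed bone marrow suppression that can be experienced with MMC". Palliative radiation for pain is taken out of the 14 days and given no interval of its own.

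**Baseline scan (6.1 footnote 14; 7.1.6.1).** "Baseline tumor imaging and assessments must be performed within 28 days prior to the first ADXS11-001 infusion in the first study cycle". Section 7.1.6.1 repeats the window. Neither place says that the scan must follow the last prior treatment or any radiation given before the first dose.

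**Treatment during the study (5.5.2).** The section opens "Subjects are prohibited from receiving the following therapies during the Screening and Treatment Phase of this trial", and the first item covers anticancer therapy, including chemotherapy and radiation. It then adds: "However occasional radiation therapy for palliation of pain is allowed". A note permits radiation to a symptomatic solitary lesion, or to the brain, after consultation with the sponsor.

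**Response (7.1.4.2 to 7.1.4.4).** Lesions in a previously irradiated area are non-measurable unless new since the radiation. Targets are fixed at baseline, and PR is a fall of at least 30% in the target sum from baseline.

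**Prior therapy (5.1.1 #2).** "Must have received at least one line of therapy for their metastatic disease", or the investigator judges the subject not an optimal candidate for chemotherapy. Progression on or after the last line is not required.

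**The concern.** The trial has one arm, and tumor response by RECIST 1.1 is a primary endpoint. Shrinkage from any other anticancer treatment after the reference scan is therefore credited to ADXS11-001, with no control arm to offset it. Local radiation is the one such treatment that the protocol permits both between the baseline scan and first dose and throughout treatment, and the response rules do not mention it.

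A second, weaker route is late shrinkage from non-MMC therapy that ended before the scan. That therapy may have ended as little as 14 days before first dose, and a subject still responding to it is not excluded.

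At stake are the Stage 1 decision, where a few responders decide whether the response criterion is met, and how far the reported response rate can be attributed to the drug. Measured progression could also be delayed, which would help 6-month PFS, but that effect is not quantified here.

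**Working it through.** **Step 1. Overlap between baseline scan and other treatment, in days before first dose**

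| Prior or concurrent treatment | Washout | Can it follow a day −28 scan? |
|---|---|---|
| Non-MMC standard therapy | 14 days | On #11a alone, 28 − 14 = 14 days of overlap. Under 5.5.2 with 7.1.6.1, 0 days: chemotherapy is barred in Screening, and Screening begins with the first screening evaluation, of which baseline imaging is one |
| MMC | 42 days | No: 42 > 28 |
| Palliative radiation for pain | none stated | Yes: up to 28 days before first dose, and again on treatment |

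**Step 2. Can one irradiated lesion give a PR?** Let s be its share of the baseline target sum, with the other targets unchanged. PR needs a shrinkage d of that lesion with s × d ≥ 0.30, so d ≥ 0.30/s.

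- s = 1 (single target): d ≥ 30%.
- s = 1/2: d ≥ 60%.
- s = 1/3: d ≥ 90%.
- s < 0.30: impossible from that lesion alone.

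The route is therefore open mainly to subjects with one or two targets, or one dominant target.

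**Step 3. The plan's own figures.** Section 8.2 gives 31 + 24 = 55. An exact search finds this as the Simon minimax design for 10% against 25%, one-sided alpha 0.05, power 0.90: continue with at least 4/31, succeed with at least 10/55, exact alpha 0.0422, power 0.9006. The stated average sample number also checks: 31 + 24 × (1 − 0.94992) = 32.20192. The simulated type I error and power cannot be reproduced, because the joint rates are not given.

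Section 8.2 states the Stage 1 response criterion both as 3 or more responses and as at least 10%. Since 3/31 = 9.7% and 4/31 = 12.9%, the 10% criterion needs 4. Both are shown below.

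**Step 4. Effect on Stage 1.** The documents give no frequency, so these are assumptions: true drug response rate 5%; a fraction f of subjects affected; a chance c = 20% that an affected subject who would not otherwise respond shows a spurious PR. The apparent rate is p = 0.05 + f × 0.95 × c, and the probabilities are binomial with n = 31.

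| f | p | P(≥4/31) | P(≥3/31) |
|---|---|---|---|
| 0 | 0.050 | 0.067 | 0.201 |
| 5% | 0.05 + 0.05 × 0.95 × 0.20 = 0.0595 | 0.110 | 0.280 |
| 10% | 0.05 + 0.10 × 0.95 × 0.20 = 0.069 | 0.163 | 0.362 |

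The expected number of spurious responders in 31 is about 0.3 (31 × 0.0095) at f = 5% and 0.6 (31 × 0.019) at f = 10%.

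**Step 5. Effect on the final result.** The Stage 2 hypothesis is 25%, and 0.25 × 55 = 13.75, so 14 responders are needed. With at least 4/31 in Stage 1 and at least 14/55 overall, the chance of success is below 0.0001 in all three rows.

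If the true rate is 10% and carry-over adds 2 points, P(≥4/31) goes from 0.376 to 0.520, and the chance of 14/55 from 0.001 to 0.005. Under the 10/55 cut from Step 3, which the plan does not state, it would go from 0.042 to 0.112.

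**The case against.** **A reader might infer that a site may scan on day −28, give chemotherapy on day −15 and dose on day 1.** The documents do not support this: Section 5.5.2 prohibits chemotherapy during Screening, and the baseline scan belongs to Screening under 7.1.6.1. What stands is that #11a does not refer to 5.5.2, so the bar has to be pieced together.

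**A reader might also infer that all prior chemotherapy needs only 14 days.** MMC needs six weeks, longer than the scan window.

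**Section 4.2 says of 5FU/cisplatin: "Response rates with this combination range between 40-50" percent, and it is tempting to use that as the carry-over chance.** It is the response rate to a whole regimen, not the chance of a further 30% fall after a scan taken once the regimen has ended, so it is not used here.

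**Section 7.1.4.2 could be read as removing a lesion from the targets once it is irradiated.** The text does not say so. Targets are chosen at baseline, and no step reclassifies them.

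**The route is narrow.** Bone lesions, common reasons for pain radiation or not, cannot be targets, and Step 2 shows that one lesion among several rarely suffices. This stands and argues for a small effect. A scan up to 28 days old also counts pre-dose growth as on-study change, which lowers response. The net direction of the scan window is therefore not established, but irradiating a target acts only upward on response.

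**Stage 2 opens on response or 6-month PFS.** Response inflation changes the decision only when the PFS criterion fails. This also stands.

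**Section 8.1 leaves analysis detail to a SAP.** No separate SAP text appears in the combined document, so a rule there cannot be ruled out. Section 7.1.4, where response is defined, has none.

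**Conclusion.** The gap is real and limited. As written, a target lesion irradiated for pain after the baseline scan, before first dose or on treatment, can yield a counted PR in the primary analysis. Late shrinkage from non-MMC therapy that ended before the scan is also possible.

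The size is unknown. With a true rate of 5%, a 20% chance of a spurious PR and 5% to 10% of subjects affected, the chance of meeting the 10% Stage 1 response criterion rises from 0.067 to between 0.11 and 0.16. Each of those inputs is an assumption.

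A reader might infer that the trial's final conclusion is at risk, or that eligibility must require documented progression on the last line. Neither is supported. The effect on a 14/55 result is negligible, and entry without documented progression is a debatable eligibility trade-off rather than an error. This is a cheap improvement that makes the response rate easier to attribute to ADXS11-001.

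**What to change.** 1. In 6.1 footnote 14 and 7.1.6.1, require the baseline scan to follow the last prior anticancer therapy and any palliative radiation given before first dose, still within 28 days of first dose. Add a cross-reference from 5.1.1 #11a to 5.5.2.
2. In 7.1.4.3 and 8.3.1, state that a target lesion irradiated after the baseline scan cannot support CR or PR in the primary analysis. From the date of radiation the subject is not counted as a responder unless response was already documented, and stays in the denominator.
3. Leave eligibility as it is. Record progression status on the last prior therapy and report a sensitivity analysis of response and 6-month PFS by that status. Section 7.1.1.5 already collects prior treatments and best responses, so this adds one item. Section 5.5.1 already captures concomitant therapies and procedures, which identifies the subjects for item 2.

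None of this changes whether or when radiation is given, the dosing or the sample size. The cost is protocol wording, a few later or repeat baseline scans, and possibly a slightly lower observed response rate.

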5.1.2 Exclusion Criteria

The subject must be excluded from participating in the trial if the subject:

1. Has not recovered (e.g., Grade ≤ 1 or at baseline) from AEs, with the exception of alopecia or Grade ≤ 2 neuropathy, due to a previously administered agent.
 2. Has a diagnosis of immunodeficiency.
 3. Has known additional malignancy that is progressing or requires active treatment. Treatment of an additional malignancy with chemotherapy, immunotherapy, biologic or hormonal therapy must have occurred 2 years prior. Concurrent use of hormones for non-cancer-related conditions (e.g., insulin for diabetes and hormone replacement therapy) is acceptable.
 - a. Note: Local treatment of isolated lesions for palliative intent (e.g., by local surgery or radiotherapy), basal cell carcinoma of the skin, or squamous cell carcinoma of the skin, or ductal carcinoma in situ of the breast that has/have been surgically cured is acceptable.
 4. Has known active CNS metastases and/or carcinomatous meningitis. Subjects with previously treated brain metastases may participate provided the metastases are stable (without evidence of progression by imaging for at least 4 weeks prior to the first dose of study treatment and any neurologic symptoms have returned to baseline), have no evidence of new or enlarging brain metastases, and are not using steroids for at least 7 days prior to the first dose of study treatment.
-

5. Has concurrent unstable or uncontrolled medical condition (e.g. active uncontrolled systemic infection, poorly controlled hypertension or history of poor compliance with an anti-hypertensive regimen, unstable angina, congestive heart failure, uncontrolled diabetes) or other chronic disease, which in the opinion of the investigator, could compromise the patient or the study.
 6. Has an active autoimmune disease requiring systemic treatment within the past 3 months or a documented history of clinically severe autoimmune disease, or a syndrome that requires systemic steroids or immunosuppressive agents.
 - a. Subjects with vitiligo or resolved childhood asthma/atopy would be an exception to this rule.
 - b. Subjects that require intermittent use of inhaled steroids, bronchodilators or local steroid injections may be allowed with sponsor approval.
 - c. Subjects with hypothyroidism stable on hormone replacement or Sjorgen's Syndrome will not be excluded from the study.
 7. Has an active infection requiring systemic therapy. Prior to dosing with study treatment(s), the subject must be at least 5 half-lives from their last dose of antibiotic.
 8. Has any other serious or uncontrolled physical or mental condition/disease that, as judged by the investigator, could place the patient at higher risk derived from his/her participation in the study, could confound results of the study, or would be likely to prevent the patient from complying with the requirements of the study or completing the study.
 9. Has known psychiatric or substance abuse disorders that would interfere with cooperation with the requirements of the trial.
 10. Subject has implanted medical device(s) that pose a high risk for colonization and/or cannot be easily removed (e.g., prosthetic joints, artificial heart valves, pacemakers, orthopedic screw(s), metal plate(s), bone graft(s), or other exogenous implant(s)).
 - a. Note: More common devices and prosthetics which include arterial and venous stents, dental and breast implants and venous access devices (e.g. Port-a-Cath or Mediport) are permitted. Subjects with any other devices or implants must be approved by Sponsor prior to participation.
 11. Any patient currently requiring or anticipated to require tumor necrosis factor (TNF) blocking agent (e.g., infliximab) therapy for diagnosis of rheumatologic disease or inflammatory bowel disease (e.g., ankylosing spondylitis, Crohn disease, plaque psoriasis, psoriatic arthritis, rheumatoid arthritis or ulcerative colitis).
 12. Patients who are currently receiving or who have received any PI3K inhibitor within 30 days prior to registration.
-

13. Subject has a contraindication (e.g. sensitivity/allergy) to trimethoprim/sulfamethoxazole **and** ampicillin.
14. Has a known history of human immunodeficiency virus (HIV) (HIV 1/2 antibodies).
15. Has known active hepatitis B or hepatitis C.
16. Has a known allergy to any component of the study treatment(s) formulations.
17. Has contraindication to administration of NSAIDs.
18. Has undergone a major surgery, including surgery for a new artificial implant and/or medical device which is permitted by the protocol, within 6 weeks prior to the initiation of ADXS11-001 treatment
 - a. Note: If the subject had a major surgery, all toxicities and/or complications from the intervention must have recovered to at least the baseline or Grade 1 prior to the initiation of ADXS11-001 study therapy. Consult with the Sponsor prior to enrolling subjects on the study who recently had a major surgery or have a new artificial implant and/or medical device.
19. In the opinion of the investigator has rapidly progressing disease, OR has life expectancy of <6 months, OR would be unable to receive at least 1 cycle of therapy.

